## 4. Statistical Analysis Plan

### Feasibility

The primary outcome will be intervention and study feasibility, defined *a priori* as 1) enrollment rate of  $\geq 50\%$  of eligible infants and 2) complete data collection rate of  $\geq 80\%$ .

Enrollment rate will be computed as the number of infants enrolled divided by the number of eligible infants screened. Complete data collection will be defined as all eligible infant, parent, and clinician data points collected for a given case; data points for which a participant withdraws prior to relevant data collection will be excluded.

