The infant's chart will be reviewed and relevant data extracted. We will also document recruitment feasibility data. Parent baseline surveys will include demographic information and measures of psychological distress. Post-intervention surveys will be given to parents and clinicians following use of the tool. Clinician surveys will include measures of decision aid acceptability. Parent surveys will include measures of decision aid acceptability, decisional satisfaction, conflict and regret, perception of feeling heard and understood, preparation for decision making, and psychological distress.

Parents and clinicians will be invited to complete semi-structured interviews, with content targeting acceptability of the decision aid. Survey data will be collected and stored via REDCap. Qualitative data will be analyzed using NVIVO.

Study participants.

Study participants will include infants, parents, and clinicians. Study team members will screen unit lists for potential eligible patients.

Infant inclusion criteria will include 1) age < 1 year, 2) admission to a critical care unit, and 3) an anticipated serious health care decision, defined as 1) a decision about

initiating, not initiating, or withdrawing life sustaining treatment or chronic life-sustaining treatment (e.g. tracheostomy) and/or 2) a decision about major surgery and/or medical therapy.

All parents of eligible infants will be considered for inclusion. Parent exclusion criteria will include 1) age < 18 years, 2) hearing or speech impairment, and 3) non-English speakers.

All clinicians of eligible infants will be considered for inclusion.

Subject Recruitment and Compensation.

We anticipate up to 40 infants, 60 parents, and 40 clinicians will be enrolled in this study.

Patients and parents: We will recruit from the Duke Intensive Care Nursery, Pediatric Intensive Care Unit, and Pediatric Cardiac Intensive Care Unit.

A study team member will communicate with the unit about 1) eligible patients and 2) approaching the family about their willingness to speak with research staff about the study. A waiver of HIPPA authorization has been requested to allow identification of prospective participants. A member of the study team will approach eligible families to introduce the study to the family. For infants enrolled, parents will be compensated \$100 for completion of all study procedures. Clinicians will be compensated \$50 for completion of all study procedures.

Study Intervention.

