### Study Objectives, Aims, and Hypotheses

Primary/ Secondary Outcomes	Aim/Objective	Hypothesis
Primary	Compute enrollment rate.	We expect the proportion of enrolled infants to be at least 50%.
Primary	Compute complete data collection rate.	We expect the proportion of enrolled families with data collected to be at least 80%.
Secondary	Describe decision aid acceptability, stratified by parent and clinician.	Descriptive objective, no hypothesis testing
Secondary	Describe pre- and post- parent psychological distress, stratified by parent.	Descriptive objective, no hypothesis testing
Secondary	Describe pre- and post- decision (as appropriate) outcomes, stratified by parent.	Descriptive objective, no hypothesis testing
Sample description	Describe infant characteristics, parent demographics, and clinician demographics.	Descriptive objective, no hypothesis testing

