## **Exclusion Criteria**

- Parent exclusion criteria will include 1) age < 18 years, 2) hearing or speech impairment, and 3) non-English speakers.

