## **3. Outcomes, Exposures, and Additional Variables of Interest**

### **Outcomes**

Outcome	Definition/Descriptions	Variables and Source
Enrollment rate	Percentage of eligible infants enrolled.	screening log
Complete data collection rate	Complete data collection defined as all eligible infant, parent, and clinician data points collected for a given case; data points for which the participant withdrew prior to relevant data collection excluded	data collection log
PrepDM score	The preparation for decision making (PrepDM) scale evaluates parents' perceptions of how useful the decision aid was in preparing them to communicate with their child's health care team and make a decision. The 10-item survey uses a 5-point Likert scale. In accordance with the user manual and other studies, we will convert item responses to integers from 1 to 5, calculate the average, subtract 1 from average, and multiply by 25 to give a final score from 0 to 100. Higher scores indicate a higher perceived level of preparation for decision making.	prepdm_score (to be derived)  Components: decision_present, decision_prep, consider_pros_cons, importance_pros_cons, depends_values, organize_thoughts, decision_involvement, questions_to_ask, discuss_values, prep_future_convos

Found this decision guide to be helpful		guide_helpful
would recommend this decision guide to other parents making decisions about their child's health care		rec_to_parents
would use this decision guide again if I need to make future decisions about my child's health care		would_use_again
Promis t-score	We will measure scores for the following PROMIS domains: Short Form v2.0 Physical Function 4a, Short Form v1.0 Emotional Distress - Anxiety 8a, Short Form v1.0 Emotional Distress - Depression 8a, Short Form v1.0 Fatigue 4a, Short Form v1.0 Sleep Disturbance 4a, Short Form v2.0 Ability to Participate in Social Roles and Activities 4a, Short Form v1.1 Pain Interference 4a, and Numeric Rating Scale Pain Intensity 1a. The default calibration sample will be used for all scores.	stress_promis_tscore (to be derived)

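### Does the enrollment-rate denominator need to say how infants with no includable parent are counted?

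*SAP*

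**What the plan says.** Enrollment rate is one of two primary feasibility outcomes. The Outcomes table in SAP section 3 defines it as "Percentage of eligible infants enrolled" and names the screening log as its source. The Feasibility part of section 4 gives the formula: "Enrollment rate will be computed as the number of infants enrolled divided by the number of eligible infants screened". The criterion is 50% or more.

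SAP section 2 lists three inclusion criteria, all labeled as infant criteria: age, critical care admission and an anticipated major decision. The next heading holds a single entry, labeled as applying to parents: "Parent exclusion criteria will include 1) age < 18 years, 2) hearing or speech impairment, and 3) non-English speakers".

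The protocol (Study participants) gives the same two lists and joins them with "All parents of eligible infants will be considered for inclusion". Under Subject Recruitment and Compensation, the first step for study staff is to "communicate with the unit about 1) eligible patients and 2) approaching the family about their willingness to speak with research staff". The same paragraph adds: "A member of the study team will approach eligible families to introduce the study to the family".

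No sentence in either document says how an infant with no includable parent is counted in the rate.

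**The concern.** The tool is completed by a parent, and infants are enrolled together with their parents. An infant whose parents are all excluded therefore cannot be enrolled as the study is described. Such an infant could be kept in the denominator, which makes the rate a measure of reach. The infant could also be left out, which makes it a measure of recruitment among families who could have joined. Both are legitimate quantities, and they answer different questions.

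The wording gives the narrower count some support. The protocol speaks of approaching eligible families, and the parent exclusions are the only entry under the SAP's exclusion heading, in the same section as the infant criteria. The two primary hypotheses also use different units, infants for enrollment and families for data completeness ("We expect the proportion of enrolled families with data collected to be at least 80" percent).

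The protocol's Measures section says feasibility must be shown before a randomized trial. If the two counts gave results on opposite sides of 50%, the same screening log could support opposite statements about a primary outcome.

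**Working it through.** **Which reading the text supports.**

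| Place | What it bears on | Points to |
|---|---|---|
| SAP sections 3 and 4 | The rate itself, stated for eligible infants | Infant criteria |
| SAP section 2, inclusion list | The only criteria labeled for infants | Infant criteria |
| Protocol, Study Overview | Screening covers critically ill infants facing a serious decision | Infant criteria |
| Protocol, Study participants | Unit lists are screened for patients; infants are called eligible before parent exclusions apply | Infant criteria |
| Protocol, Recruitment | Whom staff approach: eligible families | Narrower reading, weakly; it may just mean families of eligible infants |
| SAP section 2, exclusion list | Labeled as a parent list | Narrower reading, weakly |
| SAP section 1, families wording | The other primary outcome, computed after enrollment | Neither |

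The passages closest to the definition favor the three infant criteria alone.

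**How far apart the readings can be.** The plan states no derived figure to reproduce. Let c be the enrollment rate among infants with at least one includable parent, and q the share of infants meeting the infant criteria who have none. The documents give neither, so both are assumed over a range.

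- Narrow rate = c.
- Infant-only rate = c(1 - q).
- If c is below 50%, both miss the criterion.
- If c is at least 50%, they disagree only when c(1 - q) < 0.5, that is, when q > 1 - 0.5/c.

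| Assumed c | q must exceed |
|---|---|
| 52% | 1 - 0.5/0.52 = 3.8% |
| 55% | 1 - 0.5/0.55 = 9.1% |
| 60% | 1 - 0.5/0.60 = 16.7% |
| 70% | 1 - 0.5/0.70 = 28.6% |
| 80% | 1 - 0.5/0.80 = 37.5% |

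**In counts.** At the planned maximum of 40 enrolled infants, 50% is met when the denominator is at most 40/0.5 = 80.

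- With 67 enrollable infants, the narrow rate is 40/67 = 59.7%. Adding 7 with no includable parent gives 40/74 = 54.1%, met on both readings. It takes 81 - 67 = 14 such infants to reach 40/81 = 49.4%.
- With 57 enrollable infants, the narrow rate is 40/57 = 70.2%. Adding 14 gives 40/71 = 56.3%, met on both. It takes 81 - 57 = 24 to fall below 50%.
- Nearer the threshold, 36 enrolled of 80 is 45.0%. Leaving out 8 with no includable parent gives 36/72 = 50.0%, which meets the criterion.

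An infant with one excluded and one includable parent does not add to q.

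**The case for a change.** The strongest argument for a change is that a primary outcome with a fixed threshold should give one answer from one log. A statistician could reasonably drop infants who could never have been enrolled, and nothing in the SAP forbids it. The 36-of-80 example shows that the result against 50% can reverse, and the clarification would cost about two sentences.

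Part of this stands: the documents are silent on these infants, and a reversal is arithmetically possible near 50%. But silence on a subgroup does not leave the rule without a natural meaning. The argument from practicality shows that such an infant cannot be enrolled; it does not show that the infant leaves the denominator.

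The suggested remedy is also a preference. Making the parent-restricted rate primary adopts the less literal reading, and because c is never less than c(1 - q), it makes 50% easier to meet. It also needs an extra rule for families never spoken to, whose status under the parent exclusions may be unknown. The formulas above have no such third group, so they do not describe the rate that this remedy would produce. The infant-only count needs no such rule.

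**Conclusion.** No change follows. An analyst who applies the SAP as written counts screened infants meeting the three infant criteria. That gives a sound and computable rate, and it is the more cautious of the two against the 50% criterion.

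The possible effect on the primary result is real only near the threshold or with many infants lacking an includable parent. In the illustrations with 40 enrolled, that means 14 of 81 infants (17.3%) or 24 of 81 (29.6%). These figures rest on assumed values of c and q, and nothing in the documents indicates which values would apply. The outcome is an observed proportion in a single-arm feasibility study, with no formal test described. Stating the denominator when the result is reported would tell the reader which rate was used, and the plan does not have to be altered for that.

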### Decision aid acceptability, Psychological stress, and Decision outcomes

Secondary outcomes include 1) parent and clinician acceptability of the tool, 2) preparation for decision-making, as measured by the Preparedness for Decision-making Scale (PrepDM), and 3) parent psychological distress, as measured using the PROMIS. Parent and clinician acceptability will be measured using self-report questions. Additional measured outcomes include parent decisional conflict, regret, and satisfaction. Decisional conflict and regret will be measured by the Decisional Conflict Scale (DCS) and the Decisional Regret Scale (DRS). Satisfaction with decision-making was measured using the Family Satisfaction-ICU decision-making subscale.

Decision aid acceptability will be summarized separately by parent, mother and father, as well as clinician. Pre- and post-intervention parental psychological stress and decision outcomes will be described for self-identified mothers and fathers separately.

Categorical characteristics will be summarized as frequency and percent, continuous characteristics will be summarized as mean, standard deviation, median, Q1, Q3, and range. A list of all reported variables can be found in the table shells in **section 5**.

## 5. Appendix. Planned table shells:

**Table 1. Infant Characteristics**

Characteristic	Median (Range) or n (%)
Infants enrolled (n=)	
Gestational age at birth, weeks	
Age at enrollment, days	
Sex, Female	
Medical condition	
Prematurity (<37 weeks)	
Seizures	
Genetic diagnosis	
Congenital heart disease	
Neurologic diagnosis	
Interventions (%)	
Mechanical ventilation	
Surgical feeding tube placement	
Palliative care consult	
Tracheostomy placement	
Length of hospital stay, days	
Location at enrollment	
NICU	
PCICU	
PICU	
Death during study enrollment	

**Table 2. Parent Characteristics**

Characteristic	Median (Range) or n (%)
Parents enrolled (n=)	
Age, y	
Gender, Female	
Race and ethnicity	
African American	
Asian	
Hispanic/Latinx	
White	
More than one race	
Other/not reported	
Level of education	
Less than high school	
High school/GED	
Some college	
Bachelor's degree	
Associate's degree	
Graduate or professional degree	
Annual household income	
Less than \$25,000	
\$25,000-\$34,999	
\$35,000-\$49,999	
\$50,000-\$74,999	
\$75,000-\$99,999	
\$100,000-\$149,999	
Greater than \$150,000	
Not reported	
Decision Guide Use	
Shared with clinical team	
Used in family conference	

**Table 3. Clinician Characteristics**

Characteristic	Median (Range) or n (%)
Clinicians enrolled (n=)	
Age, y	
Gender, Female	
Race and ethnicity	
African American	
Asian	
Hispanic/Latinx	
White	
More than one race	
Other/not reported	
Years in practice	
Specialty	
Neonatology	
Pediatric critical care	
Pediatric neurology	
Pediatric cardiology	
Neurosurgery	
Other	
Social work	
Nursing	
Decision Guide Acceptability	
Found it to be helpful	
Would recommend to parents	
Would use again in future	

**Table 4. Decision Aid Acceptability**

Acceptability measure	Mothers	Fathers	Clinicians
Found to be helpful			
Would recommend to other parents/patients			
Would use in the future			

Categorical variables display n for Agree/Strongly agree.

**Table 5. Preparedness for Decision Making**

	Mothers	Fathers	Clinicians
PrepDM score			
PrepDM items (n agree or strongly agree, %)			
Helped recognize that decision needs to be made for child			
Prepared me to make decision for child			
Helped me think about the pros and cons of each treatment option			
Helped me think about which pros and cons are most important			
Helped me know that the decision depends on what matters most to me			
Helped me organize my thoughts			
Helped me think about how involved I want to be in making decisions			
Helped me identify questions to ask my child's doctor			
Prepared me to talk to my child's doctor about what matters most to me			
Prepared me for future conversations with my child's doctor			

Median (IQR) and n (%) for continuous and categorical variables, respectively. Categorical variables display n for Agree/Strongly agree or Quite a bit/A great deal

**Table 6. Parent well-being (PROMIS measure)**

		Baseline			Post-Intervention			Difference (Post - Pre)		
Score	Response	Baseline Mother	Baseline Father	Baseline All Participants	Post-Intervention Mother	Post-Intervention Father	Post-Intervention All Participants	Post - Pre Mother	Post - Pre Father	Post - Pre All Participants
PROMIS: Ability to Participate in Social Roles and Activities										
PROMIS: Emotional Distress – Anxiety										
PROMIS: Emotional Distress – Depression										
PROMIS: Fatigue										
PROMIS: Pain Intensity										
PROMIS: Pain Interference										
PROMIS: Physical Function										
PROMIS: Sleep Disturbance										

Median (IQR) and n (%) for continuous and categorical variables, respectively.

**Table 7. Decisional conflict, decisional regret, decision-making satisfaction, and feeling heard and understood.**

		Baseline			Post-Intervention			Difference (Post - Pre)		
Score	Response	Baseline Mother	Baseline Father	Baseline All Participants	Post-Intervention Mother	Post-Intervention Father	Post-Intervention All Participants	Post - Pre Mother	Post - Pre Father	Post - Pre All Participants
Decisional Conflict score										
Effective Decision										
Informed										
Support										
Uncertainty										
Values Clarity										
Decisional Regret score										
Family Satisfaction-ICU score										
Feeling Heard and Understood score										

Median (IQR) and n (%) for continuous and categorical variables, respectively. Categorical variables display n for Agree/Strongly agree or Quite a bit/A great deal.
